#### 7.9.3 Subgroup Analysis

The primary endpoints will be assessed by pediatric (<22 years old) and adult (≥22 years old) cohorts as defined per the FDA Guidance: Premarket Assessment of Pediatric Medical Devices (24 March 2014) [1] and by gender.

#### 7.10 Safety Evaluation

Assessment of safety is defined as assessment of:

- All procedure-related serious adverse events
- All device-related serious adverse events
- Death (all-cause, procedural, and device-related)

For assessment of safety, the CEC data will be used for analysis. The analysis cohorts are:

- All procedure-related adverse events: Catheterized cohort
- All device-related adverse events: attempted implanted cohort
- Death (all-cause, procedural, and device-related): Catheterized cohort

Adverse events will be analyzed either via survival analysis using the Kaplan-Meier method or summarized by count and percent as appropriate.

Revision 5.1

Form Medtronic

Page 18 of 24

#### **7.11 Additional Outcomes Measures**

Final analysis on the additional outcome measures will be performed when the implanted subjects have reached their 5 year endpoints, with the exception of the following endpoints, which will be analyzed in conjunction with the primary objective analysis (when all implanted subjects have reached their 6-month visit):

- Technical success at exit from catheterization lab/operating room (OR)
- Procedural success at 30 days

#### Outcome Measure #1: Technical success at exit from catheterization lab/operating room (OR)

Technical success is defined as:

- No device- or procedural-related mortality, with
- Successful access, delivery and retrieval of the delivery system, and
- Deployment and correct positioning (including minor repositioning if needed) of the single intended device, and
- No need for additional unplanned or emergency surgery or re-intervention related to the device or access procedure

The analysis cohort for technical success will be the attempted implant cohort. The percentage of subjects with technical success will be presented. If an element of the composite is missing and available elements meet the success criteria, the subject will be excluded from the analysis.

#### Outcome Measure #2: Device success out to 5 years

Device success is defined as:

- No device- or procedural-related mortality, with
- Original intended device in place, and
- No additional surgical or interventional procedures related to access or the device since completion of the original procedure (i.e., exit from the catheterization lab), and
- Intended performance of the device, as defined as:
  - Structural performance: No migration, embolization, detachment, major stent fracture, hemolysis, thrombosis, endocarditis, and
  - Hemodynamic performance: Relief of insufficiency (PR < moderate) without producing the opposite (mean RVOT gradient > 40 mmHg) as measured by continuous wave Doppler, and
- Absence of para-device complications, as defined by:

<sup>2 If a catheterization is performed for clinical purposes, the catheterization peak gradient measurement will supersede the continuous-wave Doppler measurement and be used to support the outcome measure.

Page 19 of 24

Form

Medtronic

Revision 5.1

- o PVL ≥ moderate, or
- o Erosion, or
- o RVOT or PA rupture

The analysis cohort for device success will be the attempted implant cohort. The endpoint will be reported as Kaplan-Meier estimate for device failure which will be the opposite of device success. The loglog transformed two-sided 95% confidence interval using the Peto standard error at 6 months (183 days), 1 year (365 days), 2 years (730 days), 3 years (1095 days), 4 years (1460 days) and 5 years (1825 days) will be presented.

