#### Outcome Measure #3: Procedural success at 30 days

Procedural success is defined as:

- Device success at 30 days, and
- None of the following device- or procedure-related serious adverse events:
  - o Life-threatening major bleed
  - Major vascular or cardiac structural complications required unplanned reintervention or surgery
  - Stage 2 or 3 acute kidney injury (AKI) (includes new dialysis)
  - o Pulmonary embolism
  - Severe heart failure (HF) or hypotension requiring IV inotrope, ultrafiltration, or mechanical circulatory support
  - Prolonged intubation >48 hours

The analysis cohort for procedural success will be the attempted implant cohort. The percentage of subjects with procedural success will be presented. If an element of the composite is missing and available elements meet the success criteria, the subject will be excluded from the analysis.

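### Device and procedural success can credit the Harmony with a valve or stent placed across it as an unplanned rescue before lab exit

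*SAP*

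**What the plan says.** SAP 7.11 defines three linked outcome measures, all in the attempted implant cohort. Protocol 4.3 and 12.3 give the same definitions.

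- **Technical success (Outcome Measure #1)**, judged at exit from the lab, requires "Deployment and correct positioning (including minor repositioning if needed) of the single intended device". A separate element rules out rescue in the lab, in these words: "No need for additional unplanned or emergency surgery or re-intervention related to the device or access procedure".
- **Device success (Outcome Measure #2)**, followed to 5 years, requires "Original intended device in place". Its procedure element is "No additional surgical or interventional procedures related to access or the device since completion of the original procedure (i.e., exit from the catheterization lab". It also requires freedom from related death, acceptable gradient and regurgitation, no para-device complication, and "Structural performance: No migration, embolization, detachment, major stent fracture, hemolysis, thrombosis, endocarditis". On the denominator: "The analysis cohort for device success will be the attempted implant cohort".
- **Procedural success (Outcome Measure #3)** begins "Device success at 30 days, and" and adds the absence of six kinds of related serious adverse event, one of which is "Major vascular or cardiac structural complications required unplanned reintervention or surgery".

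Neither document carries a technical failure forward into device or procedural success.

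**The concern.** Two tests present in technical success drop out of the later measures. The requirement for a *single* device becomes a requirement that the first device is in place, and the re-intervention test becomes one that starts only after exit. A valve or stent put through the Harmony as a rescue, before the subject leaves the lab, falls between them.

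From then on, echocardiography measures the Harmony and the rescue device together. If the combination works, the 5-year device-success curve credits that result to the Harmony, and the procedure is reported as a success at 30 days. Procedural success could then exceed technical success in the same cohort, and the two rates alone would not show which procedural successes had been rescued.

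These are reported results. Procedural success is analyzed with the primary objective (SAP 7.11), and device success is among the endpoints pooled with the early feasibility study (SAP 7.13).

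**Working it through.** The plan states no expected rate for these measures, so there is no figure to reproduce. The check is to apply the definitions literally to a subject who had a second valve or stent placed before lab exit.

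**Rules**

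- Technical = no related death AND access, delivery and retrieval successful AND single device correctly placed AND no unplanned in-lab surgery or re-intervention.
- Device = no related death AND first device in place AND no related procedure after exit AND no structural event AND acceptable hemodynamics AND no para-device complication.
- Procedural = Device at 30 days AND no listed related serious adverse event.

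**Results** (elements not mentioned are taken as met)

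| In-lab second valve or stent, and… | Technical | Device | Procedural |
|---|---|---|---|
| first valve retained, no structural, para-device or listed event | Fail | **Success** | **Success** |
| trigger was migration or embolization | Fail | Fail | Fail |
| first valve removed | Fail | Fail | Fail |
| trigger was RVOT or PA rupture | Fail | Fail | Fail |
| event is a listed major vascular or cardiac structural complication | Fail | **Success** | Fail |

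Only the procedure element starts at lab exit. Death, structural performance and para-device complications carry no such start, which is why rows 2 and 4 fail. Row 3 fails on the device element. Detachment is on the same structural list as migration and embolization, so it fails in the same way. Row 1 is the gap. Row 5 keeps it for device success only.

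**Scale**

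Input: the pivotal cohort of 40 (SAP 6). The number of row-1 subjects, k, is not in the documents; k = 0 to 3 is an assumption.

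Change in procedural success if row 1 is scored as failure = k/40:

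- k = 0: 0 points
- k = 1: 1/40 = 2.5 points
- k = 2: 2/40 = 5.0 points
- k = 3: 3/40 = 7.5 points

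With no other failures, k = 1 gives 39/40 = 97.5%, with an exact 95% interval of 86.8% to 99.9%. One subject's shift is small against that width.

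Forty is the implant target. The attempted implant cohort may be somewhat larger, which would make each subject worth slightly less.

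For device success, the Kaplan-Meier estimate without censoring is the simple proportion, so one day-0 failure again moves it by 1/40, provided the subject would otherwise have stayed a success to that time point. In the analysis pooled with the 20 early feasibility subjects, 1/(40 + 20) = 1.67 points. SAP 7.13 does not list procedural success among the pooled endpoints.

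**The case against.** The strongest reply is that the split is deliberate and visible. One measure is judged at lab exit, and another counts what happens afterwards. Protocol and SAP agree on this, and technical success is reported in the same cohort and at the same time as procedural success. SAP 7.7 also summarizes procedure characteristics. Device and procedural success have no performance target and enter neither primary endpoint. Most serious in-lab problems already fail, and some rescues would fail procedural success through the structural-complication item, whose reach cannot be checked because the adverse event definitions are redacted. All of this stands. It limits the size of the point but does not close row 1: technical success reported alongside does not identify which device successes rest on a second device.

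Three stronger readings are tempting, and the documents do not support them.

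- *A reader might infer that device success ignores everything before lab exit.* It does not; only the procedure element does.
- *A reader might infer that the primary efficacy result is exposed,* for example 30/40 = 75.0% against 29/40 = 72.5% around the 75% target. That requires reading an in-lab rescue as something other than a Harmony reintervention. SAP 7.9.2 and 7.14 put no post-exit start on reintervention, the table in 7.9.2.2 fails any that occurs before the 6-month window closes, and technical success itself uses the term for in-lab events. The existing wording favors Fail. The example also needs a count lying exactly on the threshold.
- *A reader might infer that technical success should become a component of device success.* It includes access and delivery-system retrieval, so an access problem would become a permanent 5-year device failure even if a single Harmony performed well throughout.

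**Conclusion.** The gap is real and narrow. A subject with an unplanned second valve or stent across a retained Harmony before lab exit, and no structural, para-device or listed event, fails technical success but is scored as both a device success and a procedural success. With a listed related serious adverse event, only device success is affected.

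The size is 2.5 points per subject on 40, and the number of subjects is unknown and possibly zero. The conclusion assumes that a Harmony with a second device inside it still counts as in place; the text does not say, but read literally it does. This is a gap in definition, not a contradiction between the documents, and it does not bear on the performance targets. It is worth closing because the sponsor has already accepted the principle: SAP 7.14 adds freedom from reintervention to the primary efficacy endpoint and says this was always intended.

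**What to change.** In SAP 7.11 and Protocol 12.3 (and the matching text in Protocol 4.3), state that an additional valve or stent placed across the Harmony during the index procedure is a device-success failure dated day 0. Procedural success then fails too, because it contains device success at 30 days. Do not make the whole of technical success a component of device success.

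Report the number of such subjects, and show both measures under the current definition as a second line for comparability. Because the SAP describes the pivotal cohort as already complete, record the change in SAP 7.14.

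In SAP 7.9.2, confirm in one sentence that the same event is scored as a Harmony reintervention, and therefore Fail.

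The cost is a protocol amendment, SAP wording, and re-scoring of what should be few subjects from procedure data already collected. The reported device and procedural success rates may fall slightly.

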Study Procedures and Assessments	
 
• Clinical assessment at pre- and post-implant, 1 month, 6 months, 1 year, and annually through 5 years
 
• Echocardiography at pre- and post-implant, 1 month, 6 months, 1 year, and annually through 5 years
 
• Cardiac magnetic resonance (CMR) at pre-implant, 6 months, 2 years, and 5 years
 
• CMR at 1 month for the mTPV25 cohort
 
• CT Cardiac Angiography at pre-implant
 
• CT Cardiac Angiography at post-implant for the mTPV 25 cohort and for TPV 25 subjects participating in the CT sub-study
 
• Fluoroscopy at implant, 1 month, 6 months, 1 year, and 5 years
 
• SF-36 at pre-implant, 1 month, 6 months, 1 year, and annually through 5 years
 

Professional Services	
 
• Independent Echocardiography Core Laboratory
 
• Independent CMR Core Laboratory
 
• Independent Explant Pathology Core Laboratory
 
• Patient Screening Committee
 
• Independent Clinical Events Committee
 
• Independent Data Monitoring Committee
 

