## 8. Study Procedures

### 8.1. Schedule of Events

Evaluation / Visit	Pre-Implant	Implant 	Discharge	1 Month	6 Months	1 Year	Annual (2-5 Years)
Visit Window	Within 24 weeks prior to Implant procedure unless otherwise specified	Implant procedure date	Prior to hospital discharge, or at 30 days post-implant if subject remains hospitalized	Between 2 and 6 weeks after implant	Between 23 and 29 weeks after implant date	Between 44 and 60 weeks after implant date	Between ±8 weeks after the implant anniversary date
Informed Consent	X						
Screening Committee Review	X						
Clinical Assessment	X		X	X	X	X	X
TPV Implant		X					
Echo	X 		X	X	X	X	X
Functional Cardiac Magnetic Resonance Imaging	X 			X 	X		To be completed at 2 & 5 Year Follow-Up
CT Cardiac Angiography	X 		X 				
Fluoroscopy		X		X	X	X	To be completed at 5 Year Follow-Up
Chest X-Ray			X				
SF-36	X 			X	X	X	X
Assessment of Adverse Event/ Device Deficiency	X	X	X	X	X	X	X

 Post-procedure care is carried out according to the standard care of the interventional cardiologist at his/her discretion.

 Clinical Assessment includes: at baseline – subject demographic, medical history, and medication assessment; at follow-up - medication assessment, review of adverse events, and device deficiencies.

 If an echo exam has been performed for routine diagnostic purposes prior to consenting, it can be used as the pre-implant echo exam, provided it was performed within 24 weeks prior to implant. The Principal Investigator must determine if the exam contains the protocol-required data and remains adequate for subject evaluation. If subject is screen failed, functional CMR imaging was used to satisfy the inclusion criteria, and pre-implant echo was not completed within window, a deviation is not required.

 If CMR imaging is contraindicated (e.g., subject has implantable cardiac rhythm device), no deviation will be required for MRI not performed.

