### Device success out to 5 years

Device success is defined as:

- No device- or procedural-related mortality, with
- Original intended device in place, and
- No additional surgical or interventional procedures related to access or the device since completion of the original procedure (i.e., exit from the catheterization lab), and
- Intended performance of the device, as defined as:
  - Structural performance: No migration, embolization, detachment, major stent fracture, hemolysis, thrombosis, endocarditis, and
  - Hemodynamic performance: Relief of insufficiency (PR < moderate) without producing the opposite (mean RVOT gradient > 40 mmHg) as measured by continuous-wave Doppler echocardiography, and
- Absence of para-device complications, as defined by:
  - PVL ≥ moderate, or
  - Erosion, or
  - RVOT or PA rupture

---

 If a catheterization is performed for clinical purposes, the catheterization peak gradient measurement will supersede the continuous-wave Doppler echocardiography measurement and be used to support the outcome measure.

The analysis cohort for procedural success will be the attempted implant cohort. The endpoint will be described by Kaplan-Meier statistics. The loglog transformed two-sided 95% confidence interval using the Peto standard error at 6 months (183 days), 1 year (365 days), 2 years (730 days), 3 years (1095 days), 4 years (1460 days) and 5 years (1825 days) will be presented.

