#### 7.4 Handling of Missing, Unused, and Spurious Data and Dropouts

Every effort will be undertaken to minimize missing data. In time-to-event outcomes drop-outs will be censored at the time of discontinuation, consistent with the Kaplan-Meier approach.

Unless otherwise specified in each objective, no statistical techniques will be used to impute missing data for continuous or categorical outcomes. If a subject's data are missing for any reason, that subject will not be included in that portion of the analysis. The number of subjects included in each analysis will be reported so that the reader can assess the potential impact of missing data.

In the case of partial dates, if only the month and year are known, the event or assessment will be analyzed as if it occurred on the 15th of that month. If only the year is known, the event or assessment will be analyzed as if it occurred on June 30th of that year. These resolutions of partial dates are subject to the restrictions that pre-procedure assessments must occur between the enrollment date and the procedure date or within the window defined in the CIP. The post-procedure events and assessments must occur no earlier than the procedure date. According to the section 6.1 of the CIP, the windows for pre-procedure assessments are:

- CMR exam (functional): within 52 weeks prior to the implant date
- Clinical evaluation: within 24 weeks prior to the implant date

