#### Outcome Measure #4: Freedom from TPV dysfunction out to 5 years

TPV dysfunction is defined as any one of the following:

[figure not shown]
- RVOT reoperation for device-related reasons
- Catheter re-intervention of TPV
- Hemodynamic dysfunction of the TPV (moderate or greater pulmonary regurgitation, and/or a mean RVOT gradient > 40 mmHg)

The analysis cohort will be the implanted > 24 hours cohort. The endpoint will be described by Kaplan-Meier statistics. The loglog transformed two-sided 95% confidence interval using the Peto standard error at 6 months (183 days), 1 year (365 days), 2 years (730 days), 3 years (1095 days), 4 years(1460 days) and 5 years (1825 days) will be presented.

This document is electronically controlled **Medtronic Controlled Information** 056-F286, Statistical Analysis Plan Template Version A

Revision 5.1

Page 20 of 24

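### The 5-year device-failure and TPV-dysfunction estimates are last read at day 1825, before about half of the permitted 5-year exam days, so on-time 5-year findings, chiefly major stent fracture, may be left out

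*SAP*

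**What the plan says.** SAP 7.11, Outcome Measure #2, defines device success as a composite. Its structural part reads "Structural performance: No migration, embolization, detachment, major stent fracture, hemolysis, thrombosis, endocarditis, and", joined to hemodynamic, reintervention, mortality and para-device criteria. The reporting rule is "The endpoint will be reported as Kaplan-Meier estimate for device failure which will be the opposite of device success", with intervals at 183, 365, 730 and 1095 days and then "4 years (1460 days) and 5 years (1825 days) will be presented". Protocol 12.3 gives the same days and says "The endpoint will be described by Kaplan-Meier statistics". Outcome Measure #4, whose components include "Hemodynamic dysfunction of the TPV (moderate or greater pulmonary regurgitation, and/or a mean RVOT gradient > 40 mmHg", is read on the same six days.

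The Protocol's Schedule of Events (8.1) sets the window for the annual visits at years 2 to 5: "Between ±8 weeks after the implant anniversary date". The Synopsis lists "Fluoroscopy at implant, 1 month, 6 months, 1 year, and 5 years", and the schedule agrees. No fluoroscopy is scheduled between year 1 and year 5, although Protocol 8.7.1 allows for unplanned radiography.

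On dating, SAP 7.4 says "In time-to-event outcomes drop-outs will be censored at the time of discontinuation, consistent with the Kaplan-Meier approach" and gives a convention for partial dates. Neither document says whether a failure detected at a visit takes the exam date or a nominal visit day. No readable section of the SAP plans a separate summary of frame fracture.

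**The concern.** A 5-year estimate should contain what the 5-year visit finds. Read literally on actual exam dates, this one stops just before the anniversary, so an exam held exactly on the anniversary is already too late. Earlier reads also cut through their own visit windows, but a later read picks up what they leave out. Nothing follows day 1825.

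Fracture is the component most exposed. Echocardiography is annual, so a hemodynamic failure has had several earlier chances to be seen. A fracture that developed without symptoms after year 1 has one scheduled chance, and about half of the permitted dates for that exam lie beyond the last read. The day-1825 figure would then reflect whether visits ran early or late as well as how many frames fractured. That would blur a 5-year durability statement.

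**Working it through.** **1. The plan's read days.** 365 × 1, 2, 3, 4, 5 = 365, 730, 1095, 1460, 1825, and 365/2 rounded up = 183. All six stated days reproduce, so the plan counts 365-day years.

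**2. The anniversary by calendar.** Five calendar years contain one or two leap days: 1825 + 1 = 1826 or 1825 + 2 = 1827. Enumerating start dates from 2001 to 2089 gives day 1826 for about 75% and day 1827 for about 25%, never 1825.

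**3. The share of the window after day 1825.** The window is the anniversary ± 56 days, or 113 days.

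| Anniversary | Window | Days after 1825 | Share |
|---|---|---|---|
| 1826 | 1770–1882 | 57 | 50.4% |
| 1827 | 1771–1883 | 58 | 51.3% |
| 1825 (365-day years) | 1769–1881 | 56 | 49.6% |

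The leap days barely matter; the window width does. For comparison, the 6-month window (weeks 23–29, days 161–203) has 20 of 43 days after day 183, and the 1-year window (weeks 44–60, days 308–420) has 55 of 113 after day 365.

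**4. What this could do to the estimate.** The documents give no fracture rate, so these inputs are assumptions: a share p of subjects has a fracture first seen at the 5-year exam and dated there; a share f of exams falls after day 1825; fracture is taken alone.

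- Event-free subjects censored at their 5-year exam: the read at day 1825 is about 1 − f^p, because the risk set falls from N to fN as exams are held.
- No censoring before day 1825: the read is (1 − f)p.

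With exams spread evenly (f = 57/113 = 0.504):

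| p | 1 − f^p | (1 − f)p |
|---|---|---|
| 5% | 3.4% | 2.5% |
| 10% | 6.6% | 5.0% |
| 20% | 12.8% | 9.9% |

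Simulation with 40 subjects agrees with the middle column (3.3%, 6.5% to 6.7%, 12.7%), and 55 subjects give nearly the same. In counts, on average 1, 2 or 4 of 2, 4 or 8 fractures fall after day 1825.

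Visit timing alone moves the figure. At p = 10% with censoring at the exam, the simulated read is 12.7% if a quarter of exams are late and 2.8% if three quarters are. It can therefore exceed the true share as well as fall short of it.

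**5. Masking by an earlier failure.** A time-to-first-failure curve cannot show a fracture found after, say, an earlier echo failure. Take constant 5-year hazards, with fracture h and other failures split equally into non-terminal a and terminal b. The expected share masked is h/(h+b)·(1 − e^(−5(h+b))) − h/(h+a+b)·(1 − e^(−5(h+a+b))). With other failures at 10% to 40% and fracture at 5% to 20%, this is 0.05 to 0.8 of 40 subjects: small.

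**6. Does the remedy work?** Take 40 subjects, 4 fractures, and 36 event-free subjects of whom 18 are examined before day 1825.

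- Move only the 4 findings to day 1825 and leave the 18 censored at their exams: 4/(4 + 18) = 18%.
- Keep actual dates and read at day 1883, with everyone censored at the exam: the expected read is 1 − Π(1 − 0.10/i) for i = 1 to 40, about 35% with one exam per day, because the risk set empties.
- Move findings and event-free subjects together: 4/40 = 10%.

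The censoring time must therefore move with the findings.

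**The case against.** The strongest reply is that the loss is conditional. It occurs only if visit-detected failures are dated at the exam, and the SAP does not say so. A programmer who assigns findings to nominal visits would remove it. The listed days are also only those at which intervals are presented; nothing says the curve ends there. This stands, and it is why the point is put conditionally. But nominal dating is unstated, and the reads are given as day counts.

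Second, fractures may be reported elsewhere. SAP 7.10 defines its scope by serious events but also assigns a cohort to all device-related adverse events, and the CEC adjudicates endpoint-related events. A reader might infer that silent fractures will go unreported. The documents do not support that: the adverse event definitions, code list and radiography protocol are redacted, so whether an imaging-only fracture becomes an adverse event cannot be determined. The SAP also expects analyses beyond the plan, although that clause commits to none.

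Third, one might infer that half of all late fractures will be missed. The 50% is a share of permitted days, not of exams; the share of exams depends on actual visit dates. Nor can one say that Outcome Measure #4 confines the problem to structural findings, since it has the same last read.

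Finally, masking by an earlier failure belongs to any composite of this kind and is small here.

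**Conclusion.** The point holds in a limited form and is minor. It is certain from the text that the last read is day 1825, that about half of the permitted 5-year exam days come later, and that Outcome Measures #2 and #4 share this. It is conditional that on-time findings are lost: this requires dating at the exam. Under even spread, and an assumed 5% to 20% of subjects with a fracture first seen at the 5-year exam, the day-1825 read is about half to two thirds of the true share. The real figure depends on visit dates and on a fracture rate that the documents do not give. Both outcomes are descriptive additional measures, and no primary conclusion is affected.

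**What to change.** **(a)** For Outcome Measures #2 and #4, state that the 5-year estimate includes every exam held in the Protocol window. The simplest rule assigns in-window 5-year findings to the nominal 5-year visit, and gives event-free subjects seen in the window the same day, with failures counted before censorings. Clinically dated events keep their own dates. The alternative is an added read at the window close (day 1883), with event-free completers carried to that day rather than censored at their exam. Make the same change in Protocol 12.3.

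**(b)** Under Outcome Measure #2, add one descriptive table of major frame fracture at 1 month, 6 months, 1 year and 5 years: number with the finding, number assessed, and exact 95% interval. Count any in-window exam, whether or not the subject had an earlier non-terminal failure. SAP Outcome Measure #6 already summarises CMR by visit in this way.

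**Cost.** No new exams: one dating rule and one small table. The 5-year failure figure may come out slightly higher. Intervals will be wide (2/40 gives 0.6% to 16.9%; the upper limit is 8.8% for 0/40 and 6.5% for 0/55). The table shows fracture present at the exam, not when it occurred.

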### 8.7.1. Unplanned Visits

Unplanned subject visits that are not detailed in **Section 8.1. Schedule of Events** and are deemed necessary in order to evaluate the Harmony TPV are considered unplanned visits for the purposes of the protocol and do not need to take place at the study site. Additionally, only data that can be obtained by the study sites are required to be reported. Potential relevant unplanned procedures include:

- Clinical assessment
- Echocardiography
- CMR
- CT cardiac angiography
- Radiography

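### Device success counts major stent fracture as a failure and is estimated at 2, 3 and 4 years, but no fluoroscopy is scheduled between 1 and 5 years, so those estimates may be too favourable.

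*SAP*

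**What the plan says.** **Endpoint.** Device success is defined alike in SAP 7.11 (Outcome Measure #2) and protocol section 12.3. Its structural part reads "Structural performance: No migration, embolization, detachment, major stent fracture, hemolysis, thrombosis, endocarditis, and". Haemodynamic performance, further procedures and para-device complications are separate parts.

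**Estimator.** The SAP states: "The endpoint will be reported as Kaplan-Meier estimate for device failure which will be the opposite of device success". The curve is read at 6 months (day 183) and 1 year (day 365), and then: "2 years (730 days), 3 years (1095 days), 4 years (1460 days) and 5 years (1825 days) will be presented".

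**Imaging of the frame.** The protocol synopsis has "Fluoroscopy at implant, 1 month, 6 months, 1 year, and 5 years". In the annual (2 to 5 years) column of the Schedule of Events (section 8.1), the fluoroscopy entry is "To be completed at 5 Year Follow-Up". Chest X-ray is listed at discharge only. CT is listed before implant and, for some subjects, after implant.

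**Other scheduled imaging.** The synopsis gives "Echocardiography at pre- and post-implant, 1 month, 6 months, 1 year, and annually through 5 years" and "Cardiac magnetic resonance (CMR) at pre-implant, 6 months, 2 years, and 5 years". The Schedule of Events labels the CMR as functional.

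**The concern.** A Kaplan-Meier curve treats a subject as event-free until an event is recorded. For fracture, a recorded event needs a view of the frame, and three of the six reporting times (years 2, 3 and 4) have no scheduled fluoroscopy. A subject whose frame fractured in year 2 without symptoms or a change on echo would still count as a device success at years 2, 3 and 4. The fracture would enter the curve at the 5-year film, or never if the subject left the study first.

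At stake is how the durability result is read. Device success is the 5-year outcome that includes frame integrity; freedom from TPV dysfunction (Outcome Measure #4) has no fracture component. Its 2 to 4 year values would carry an unstated gap in assessment.

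**Working it through.** The documents give no fracture rate, expected device-success rate or sample size calculation, so there is no planned figure to reproduce. The check has four steps.

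**1. Reporting days against the schedule** (SAP Outcome Measure #2; protocol section 8.1)

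| Estimate | Day | Fluoroscopy scheduled | Other scheduled imaging |
|---|---|---|---|
| 6 months | 183 | yes | echo, CMR |
| 1 year | 365 | yes | echo |
| 2 years | 730 | no | echo, functional CMR |
| 3 years | 1095 | no | echo |
| 4 years | 1460 | no | echo |
| 5 years | 1825 | yes | echo, functional CMR |

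The gap between scheduled fluoroscopies is 1825 − 365 = 1460 days, or 4 years. Days 730, 1095 and 1460 all lie inside it.

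**2. Rules that might cover the gap**

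- SAP 7.4 censors drop-outs at discontinuation. Its general exclusion for missing data is written for continuous and categorical outcomes, and a film that was never scheduled is not a missing value.
- Outcome Measures #1 and #3 say what happens when an element of the composite is missing. Outcome Measure #2 does not.
- No interval-censored method is given.

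A subject not imaged for fracture therefore stays in the risk set as event-free. The error has one direction: reported success can be too high, never too low.

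**3. Size at years 2 to 4**

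Assume a constant silent major fracture rate h per year. Among subjects clear at the 1-year film, the share with an unseen fracture at year t is 1 − exp(−h(t − 1)). For example, at h = 0.02 and t = 4: 1 − exp(−0.06) = 5.8%.

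| Assumed h per year | Year 2 | Year 3 | Year 4 |
|---|---|---|---|
| 0 | 0 | 0 | 0 |
| 0.5% | 0.5% | 1.0% | 1.5% |
| 1% | 1.0% | 2.0% | 3.0% |
| 2% | 2.0% | 3.9% | 5.8% |
| 5% | 4.9% | 9.5% | 13.9% |

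In 40 subjects, the expected number unseen at year 4 is 40 × 0.0296 = 1.2 at 1% a year and 40 × 0.0582 = 2.3 at 2%. The chance of at least one, 1 − (1 − p)^40, is 70% and 91%.

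This formula ignores subjects who have already failed for another reason. A simulation (40 subjects, 2000 runs) assumed 3% a year other failures, 3% a year drop-out, and fractures seen only at scheduled fluoroscopies spread evenly over the visit windows. It gave this overstatement of device success, in percentage points:

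| Assumed h per year | Year 2 | Year 3 | Year 4 | Year 5 (day 1825) |
|---|---|---|---|---|
| 1% | 0.9 | 1.8 | 2.6 | 1.6 |
| 2% | 1.7 | 3.3 | 4.9 | 3.3 |
| 5% | 4.4 | 8.4 | 11.8 | 7.5 |

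Hand check at 2%, year 4: no other failure by year 4, exp(−0.12) = 0.887; no fracture by year 1, exp(−0.02) = 0.980; unseen since then, 0.0582. The product is 0.887 × 0.980 × 0.0582 = 0.051, or 5.1 points against the simulated 4.9.

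**4. The 5-year reading**

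The annual window is ±8 weeks, or 56 days, so the 5-year visit falls on days 1769 to 1881. The curve is read at day 1825. A film taken on days 1826 to 1881 comes too late for that reading, and a subject who leaves before the visit is never filmed. This is why the simulated error at year 5 is not zero.

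**The case against.** The strongest objection is that the bias needs silent major fractures, and the text that would settle whether they can occur is blacked out. The adverse event definitions (Appendix II) and the radiography protocol (Appendix V) are redacted. If a fracture is major only when it has a clinical or haemodynamic consequence, annual echo and adverse event collection until study exit would find most cases. This stands. Listing fracture apart from haemodynamic failure and reintervention suggests that it counts by itself, but does not prove it. A reader might infer that the 2 to 4 year estimates are certainly too favourable; the documents support only that they may be.

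Second, other imaging may find some fractures. Protocol section 8.7.1 lists radiography and CT among possible unplanned procedures, but for visits "deemed necessary in order to evaluate the Harmony TPV are considered unplanned visits", which would tend to find fractures that have shown themselves. The footnotes to the Schedule of Events tie CT to discharge for mTPV 25 sub-study subjects, but say only post-implant for TPV 25 sub-study subjects, under the redacted Appendix XII. Later CT in some of them cannot be ruled out. These points reduce the possible bias without closing the gap for the whole cohort.

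Third, a reader might infer that device success is unanswered at three of its six time points. That goes too far. Death, reintervention, device in place, regurgitation, gradient and clinically evident events are still followed at years 2 to 4. One component of many lacks scheduled imaging.

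Finally, dating an event to the visit that detects it is a common limit of Kaplan-Meier curves. That is so, but for the echo components the delay is about a year, whereas here it reaches four.

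**Conclusion.** The concern holds in this form: the 2, 3 and 4 year device-success estimates include no scheduled look for fracture, nothing in the SAP allows for that, and any resulting error favours the device. At assumed silent rates of 1% to 2% a year it is about 1 to 2 points at year 2 and 3 to 6 points at year 4, or 2.6 to 4.9 points at year 4 with the assumed other failures and drop-out. These sizes rest entirely on assumed constant rates, and the bias is zero if no major fracture is silent.

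A reader might also infer that four years of hidden fractures would appear as one full step at year 5, 1 − exp(−0.08) = 7.7 points at 2% a year. The planned day-1825 reading would not show all of it: some subjects fail or leave earlier, and some films fall after that day. The 5-year figure can itself be too favourable, by 1.6 to 3.3 points in the simulation at 1% to 2%.

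The outcome is an additional measure without a performance target. Neither primary endpoint uses fracture. The point merits a change to the SAP before the 5-year analysis, but it does not threaten the primary result.

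**What to change.** Change the analysis and labelling in Outcome Measure #2; no new imaging is needed.

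1. Keep every detected fracture as a failure in the composite at all time points. Dropping the component at years 2 to 4 would return subjects with a known fracture to success and could make reported success rise after year 1.
2. Label the 2, 3 and 4 year estimates as including no scheduled fracture imaging.
3. Report major stent fracture separately by fluoroscopy visit, as number fractured over number imaged. Treat a fracture first seen on the 5-year film as interval-censored between the last clear fluoroscopy and that film (for example, a Turnbull estimate).
4. Read the 5-year composite at the 5-year visit, or at the close of its window, so that the 5-year film is included. The visit-based reading is cleaner if follow-up ends at that visit: the risk set shrinks through the window, and one late finding would then make a large step.

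The cost is SAP wording, one extra estimate that will be imprecise in about 40 to 55 subjects, and a stated limitation on the 2 to 4 year figures.
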